### 8.2.10 Compliance (Medication Adherence)

A day within the study will be considered an On-Therapy day if the subject receives any dose of study medication. The number of Days Should be on Therapy is the total number of days from the first day of study medication to the date of the last dose of study medication. For each subject, percent compliance will then be calculated (separately for pembrolizumab and lenalidomide for Cohort 5) using the following formula:

$$\text{Percent Compliance} = \frac{\text{Number of Days on Therapy}}{\text{Number of Days Should be on Therapy}} \times 100.$$

Summary statistics will be provided on percent compliance for the FAS population.

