#### **5.2.2 Timing of Dose Administration**

Pembrolizumab should be administered on Day 1 of each cycle for subjects receiving pembrolizumab monotherapy after all procedures/assessments have been completed as detailed on the Trial Flow Chart (Section 6.0). Pembrolizumab may be administered up to 3 days before or after the scheduled Day 1 of each cycle due to administrative reasons.

All trial treatments will be administered on an outpatient basis. Administration during in-patient hospitalization requires Sponsor consultation.

Pembrolizumab will be administered as a 30 minute IV infusion. Sites should make every effort to target infusion timing to be as close to 30 minutes as possible. However, given the variability

of infusion pumps from site to site, a window of -5 minutes and +10 minutes is permitted (i.e., infusion time is 30 minutes: -5 min/+10 min).

The Pharmacy Manual contains specific instructions for pembrolizumab dose calculation, reconstitution, preparation of the infusion fluid, and administration.

Subjects in Cohort 5 (DLBCL) will receive pembrolizumab 200 mg administered intravenously once every 21 days in combination with lenalidomide taken orally once daily for 21 days + 7 days off. The cycle length is 28 days. After RP2D is established for Cohort 5 (DLBCL), treatment should continue for 26 cycles or until confirmed disease progression or unacceptable toxicity.

Because a subject treated with PD-1 inhibitors may have pseudoprogression of disease (there is progression per imaging, but the subject is clinically stable or improving), confirmation of progression should be conducted as follows:

After the first documentation of progression at Week 12, it is at the discretion of the investigator to keep a clinically stable subject on trial treatment or to stop trial treatment until a disease response assessment performed 4 to 6 weeks later confirms progression.

Clinical stability may be defined as:

- 1) Absence of symptoms and signs indicating clinically significant progression of disease (including worsening of laboratory values) with the exception of M-protein elevation for the multiple myeloma cohort.
- 2) No decline in ECOG performance status.
- 3) Absence of rapid progression of disease or progressive tumor at critical anatomical sites (e.g., cord compression) requiring urgent medical intervention.

Subjects that are deemed clinically unstable are not required to have a confirmation assessment.

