### 5.2.3 Extent of Treatment

- Subjects receiving pembrolizumab monotherapy who experience a partial response or have SD may remain on treatment until unacceptable toxicity or progression. Subjects receiving pembrolizumab monotherapy Q3W may receive up to 35 doses; subjects receiving pembrolizumab monotherapy Q2W may receive up to 52 doses.
- Per the investigator's discretion, subjects receiving pembrolizumab monotherapy who achieve a CR or sCR (MDS subjects must meet both bone marrow and peripheral blood criteria for CR; MM subjects must achieve a sCR) may stop treatment after 24 weeks provided that there are two doses received after the CR was documented. These subjects, with the exception of subjects in Cohort 2 (MM) who are not allowed, are eligible to restart treatment upon documented progression as long as they meet eligibility criteria specified in the protocol (See Section 7.1.5.2.1).
- Subjects receiving pembrolizumab monotherapy who achieve a CR or sCR and choose not to stop therapy may continue treatment until progression. Subjects receiving pembrolizumab monotherapy Q3W may receive up to 35 doses; subjects receiving pembrolizumab monotherapy Q2W may receive up to 52 doses.
- Subjects in Cohort 5 (DLBCL) who receive lenalidomide + pembrolizumab and achieve a PR or SD response may remain on treatment for up to 26 cycles or until unacceptable toxicity or progression. **Note:** Cohorts 5 has been discontinued and all subjects must stop combination treatment immediately, complete the discontinuation visit, and move into the long-term safety and survival follow-up per protocol. If clinically benefitting at time of stopping combination therapy, subjects may enter a transition period remaining on single agent lenalidomide or pembrolizumab for up to 90 days from 15-SEP-2017 and then must transition into long-term survival and safety follow-up.

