
**6.6.1 Study Dose Chart F2: Cohort 5 Diffuse Large B-Cell Lymphoma (DLBCL) (Subjects allocated to pembrolizumab 200 mg administered intravenously once every 21 days in combination with lenalidomide taken orally once daily for 21 days + 7 days off. The cycle length is 28 days.)**

	Each Cycle = 28 Days (To be repeated beyond 3 cycles)											
	Cycle 1				Cycle 2				Cycle 3			
Trial Treatment/ Cycle Day (± 3 days)	Days 1-7	Days 8-14	Days 15-21	Days 22-28	Days 1-7	Days 8-14	Days 15-21	Days 22-28	Days 1-7	Days 8-14	Days 15-21	Days 22-28
Pembrolizumab (Q3W) a	1			22			15			8		
Lenalidomide b	1 to 21				1 to 21				1 to 21			
Pill count for Lenalidomide c	1				1				1			
Pregnancy Prevention Counseling and Dispensing of Lenalidomide d	X											

Abbreviations: IV=intravenous; PO=per orem; Q3W=every 3 weeks; REMS=Risk Evaluation and Mitigation Strategy; RP2D=recommended Phase II dose.

- Pembrolizumab will be administered as 200 mg every 21 days (3 weeks) as an IV infusion over 30 minutes.
- Lenalidomide will be administered as RP2D PO, once daily on Days 1 to 21 of repeated 28-day cycles. Lenalidomide must be prescribed through and in compliance with the REVLIMID REMS™ program. Refer to local prescribing information.
- Site should document drug accountability as per their institutional guidelines.
- The Lenalidomide Education and Counseling Guidance Document must be completed for all subjects and signed by a trained counselor prior to each dispensing of lenalidomide (see Section 12.10). A copy of this document must be maintained in the subject's records for each dispense. Lenalidomide will be dispensed every 3-4 weeks as per local requirements.

Note: Cohort 5 has been discontinued and there will be no further enrollment of subjects. All subjects in Cohort 5 must stop combination treatment immediately, complete the discontinuation visit and move into the long-term safety and survival follow-up per protocol. If clinically benefitting at time of stopping combination therapy, subjects may enter a transition period remaining on single agent lenalidomide or pembrolizumab for up to 90 days from 15-SEP-2017 and then must transition into long-term survival and safety follow-up.

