- Does not have a history or current evidence of any condition, therapy, or laboratory abnormality that might interfere with the subject's participation for the full duration of the trial or is not in the best interest of the subject to participate, in the opinion of the treating investigator.

Subjects who restart treatment will be retreated at the same dose frequency as when they last received pembrolizumab for a treatment duration of a maximum of 17 cycles for subjects receiving pembrolizumab Q3W or 26 cycles for subjects receiving pembrolizumab Q2W.

Subjects in Cohort 5 (DLBCL) will be retreated at the same dose frequency as when they last received lenalidomide + pembrolizumab combination for a treatment duration of a maximum of 13 cycles.

**Note:** Subjects in Cohort 2 and Cohort 5 are no longer eligible for second course treatment phase.

Visit requirements are outlined in Section 6.0 – Trial Flow Chart.

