### 8.2.11 Extent of Exposure

Extent of Exposure for a subject is defined as number of cycles in which the subject receives any dose of study medication. Summary statistics will be provided on Extent of Exposure for ASaT population.

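### The Section 8.2.10 compliance formula divides dosing days by all calendar days, so a fully adherent pembrolizumab subject with two or more doses scores about 5–14%

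*Combined protocol and SAP*

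**What the plan says.** Section 8.2.10 builds percent compliance from two counts. The numerator rule is: "A day within the study will be considered an On-Therapy day if the subject receives any dose of study medication". The denominator rule is: "The number of Days Should be on Therapy is the total number of days from the first day of study medication", ending on the date of the last dose. The ratio is multiplied by 100, calculated separately for the two drugs in Cohort 5, and summarised for the FAS. Nothing in the section limits the denominator to scheduled dosing days or treats the days between infusions as on therapy.

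No drug in the trial is taken every day. Sections 1.0 and 5.2 (Table 4) give pembrolizumab every 2 weeks or every 3 weeks, one infusion per monotherapy cycle. Section 5.2.3 sets the maximum: "Subjects receiving pembrolizumab monotherapy Q3W may receive up to 35 doses; subjects receiving pembrolizumab monotherapy Q2W may receive up to 52 doses". Section 5.2.2 adds a window: "Pembrolizumab may be administered up to 3 days before or after the scheduled Day 1 of each cycle due to administrative reasons". The Cohort 5 dose chart (Section 6.6.1) schedules lenalidomide "once daily on Days 1 to 21 of repeated 28-day cycles". Section 7.1.5.2.1 allows retreatment after relapse from complete response, "for a treatment duration of a maximum of 17 cycles for subjects receiving pembrolizumab Q3W or 26 cycles" on Q2W.

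Two other provisions are related. Section 8.2.11 says: "Extent of Exposure for a subject is defined as number of cycles in which the subject receives any dose of study medication". Section 7.1.1.9 compares infused with prepared volume for each dose given and has lenalidomide pills counted on Day 1 of each cycle.

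**The concern.** The formula suits a drug taken daily. Applied to an intermittent infusion, it treats every planned non-dosing day as a missed day. Three things follow.

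- The score does not measure adherence. For a subject dosed on schedule, it falls with each further infusion.
- It depends on the regimen. Cohorts 2 and 4A, and Cohort 4 overall, contain both Q2W and Q3W subjects, and Section 8.1 has cohort analyses run regardless of weight-based or fixed dosing. A pooled summary would mix two scales.
- The first-to-last-dose window is not split by course. Read literally, the planned gap before retreatment also counts as days that should be on therapy.

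No other provision supplies an adherence rate. Extent of exposure counts cycles with any dose and has no scheduled denominator. The volume check covers only doses that were given, so it cannot show a missed infusion.

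**Working it through.** The plan states no compliance figure, so there is none to reproduce. The formula can be evaluated directly.

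**Inputs.** Interval g = 14 days (Q2W) or 21 days (Q3W), from Sections 1.0 and 5.2. Maximum doses 52 and 35, from Section 5.2.3. Lenalidomide on 21 of 28 days, from Table 4 and Section 6.6.1.

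**Pembrolizumab, k doses exactly on schedule, none missed.** Counting both end days, compliance = k / [g(k − 1) + 1]. Counting elapsed days, compliance = k / [g(k − 1)], which is undefined at k = 1.

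| Regimen | Doses | Inclusive | Elapsed |
|---|---|---|---|
| Q2W | 2 | 2/15 = 13.3% | 2/14 = 14.3% |
| Q2W | 10 | 10/127 = 7.9% | 10/126 = 7.9% |
| Q2W | 52 | 52/715 = 7.3% | 52/714 = 7.3% |
| Q3W | 2 | 2/22 = 9.1% | 2/21 = 9.5% |
| Q3W | 10 | 10/190 = 5.3% | 10/189 = 5.3% |
| Q3W | 35 | 35/715 = 4.9% | 35/714 = 4.9% |

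A one-dose subject scores 1/1 = 100% on inclusive days, hence the restriction to two or more doses. The 715-day span agrees with Section 12.9, where the 35th infusion falls on Cycle 26 Day 15: 25 × 28 + 15 = 715.

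**Effect of the 3-day window on the second dose (inclusive).** Q3W: 2/25 = 8.0% to 2/19 = 10.5%. Q2W: 2/18 = 11.1% to 2/12 = 16.7%.

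**Regimen dependence.** Both maximum courses span 715 days (34 × 21 + 1 = 51 × 14 + 1). Over that span, a Q2W subject who misses 13 of 52 infusions, but not the first or last, scores 39/715 = 5.5%. A fully adherent Q3W subject scores 4.9%. The Q2W subject stays ahead with up to 16 missed (36/715 = 5.03% against 35/715 = 4.90%) and ties at 17. This ordering holds for equal spans only: 39/715 = 5.45% is just below a fully adherent 7-dose Q3W subject at 7/127 = 5.51%.

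**Lenalidomide, c cycles fully taken.** 21c / [28(c − 1) + 21] gives 42/49 = 85.7% for 2 cycles, 126/161 = 78.3% for 6 and 462/609 = 75.9% for 22. Twenty-two is an upper bound: 634 days run from the issue of Amendment 05 (20-MAR-2016) to 90 days after 15-SEP-2017, and a 23rd full cycle would need 28 × 22 + 21 = 637.

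**Retreatment, Q3W, 8 doses then 17, none missed.** The documents give no gap length. The assumption here is 24 to 72 weeks (168 to 504 days) from the last dose of the first course to the first dose of the second.

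- Current formula: 25 / (7 × 21 + gap + 16 × 21 + 1) = 25/652 = 3.8% to 25/988 = 2.5%.
- Scheduled days counted straight through the gap: 25 / (25 + gap/21 − 1) = 25/32 = 78.1% to 25/48 = 52.1%.
- Scheduled days counted within each course: 25/25 = 100%.

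**After correction.** With infusions scheduled as the denominator, full adherence scores k/k = 100% at every k on both regimens. A Q3W subject who misses one of 10 infusions in mid-course scores 9/10 = 90%. Under the current formula that subject scores 9/190 = 4.7%, against 5.3% for full adherence.

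**The case against.** The strongest reply is that little depends on this. Section 8.2.10 feeds one descriptive summary. No analysis set, threshold or test uses percent compliance. Infusions are witnessed and volume-checked, and a median near 5–8% in such a trial would be noticed at programming. That limits the severity. It does not make the definition right: programmed as written, the table is wrong; programmed otherwise, it departs from the SAP without record.

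Section 8.2.10 also does not mention the second course, which has its own screening, flow charts and maximum duration, so an initial-course-only reading might have been intended. The text does not say so, and its literal window runs from first to last dose. The retreatment figures illustrate that reading under an assumed gap and dose pattern.

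The Q2W-against-Q3W ranking holds only over equal spans, as shown. The lenalidomide result matters less: Cohort 5 was stopped, and Section 8.1 allows the Cohort 2 and 5 analyses to be modified. The 22-cycle figure is a loose ceiling, because it counts from the amendment's issue date rather than from first dosing.

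Finally, changing the denominator to scheduled days leaves open how a delayed dose shifts the later schedule. That is a fair request for detail, taken up in the fix.

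**Conclusion.** The concern holds. As written, a fully adherent pembrolizumab subject with two or more on-schedule doses scores 4.9–13.3% on inclusive days, or 4.9–14.3% on elapsed days. The two-dose values move to 8.0–16.7% (inclusive) if the second dose uses the 3-day window. Because the score varies with both interval and duration, no constant rescaling recovers adherence.

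The pembrolizumab result rests only on the formula's wording and the stated schedules. The retreatment figures also rest on an assumed gap and dose pattern. The practical effect falls mainly on the compliance summaries for Cohorts 1, 3 and 4; efficacy, safety and interim results are untouched. The definition should be corrected, but it does not threaten the trial's conclusions.

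**What to change.** In Section 8.2.10, redefine the denominator as the number of scheduled dosing days under the subject's assigned regimen between first and last dose, counted within each treatment course so that the gap before retreatment is excluded.

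- **Pembrolizumab:** infusions received divided by infusions scheduled.
- **Lenalidomide:** Days 1–21 of each 28-day cycle as the denominator, with the numerator from whatever dosing records or pill counts exist.
- **Counting rules to state:** whether doses withheld under the dose-modification rules, or skipped under the permitted-interruption rule, stay in the denominator; and whether the schedule keeps its original calendar or restarts from a delayed dose.

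The cost is a rewritten definition and a few sentences. Infusions are witnessed and pills counted (Section 7.1.1.9), so the basic ratios need no new collection. There are two limits. Section 5.2.1.2 asks for the reason for an interruption only in the subject's study record, and only for interruptions unrelated to study therapy, so reasons for every missed dose may not be in the database. Daily lenalidomide intake may not be recorded either: "Site should document drug accountability as per their institutional guidelines" (Section 6.6.1). If reasons are not captured, keeping every scheduled dose in the denominator is the counting rule that needs no new data.

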### 8.2.11 Extent of Exposure

Extent of Exposure for a subject is defined as number of cycles in which the subject receives any dose of study medication. Summary statistics will be provided on Extent of Exposure for ASaT population.

## 9.0 LABELING, PACKAGING, STORAGE AND RETURN OF CLINICAL SUPPLIES

### 9.1 Investigational Product

The investigator shall take responsibility for and shall take all steps to maintain appropriate records and ensure appropriate supply, storage, handling, distribution and usage of investigational product in accordance with the protocol and any applicable laws and regulations.

Clinical Supplies will be provided by the Sponsor as summarized in [Table 22](#).

Table 22 Product Descriptions

Product Name & Potency	Dosage Form	Source/Additional Information
pembrolizumab (MK-3475) 50 mg	Lyophilized Powder for Injection	Provided centrally by the Sponsor (non-US).
pembrolizumab (MK-3475) 100 mg/ 4mL	Solution for Injection	Provided centrally by the Sponsor (US only).
lenalidomide 5, 10, 15, 20, and 25 mg	Capsules for Oral Administration	Provided centrally by the Sponsor except in regions that can source locally.  Not all dose strengths will be made available centrally from the Sponsor.  Reference the study Pharmacy Manual.

### 9.2 Packaging and Labeling Information

Clinical supplies will be affixed with a clinical label in accordance with regulatory requirements.

Vials will be provided in an open label fashion for subject dosing.

### 9.3 Clinical Supplies Disclosure

This trial is open-label; therefore, the subject, the trial site personnel, the Sponsor and/or designee are not blinded to treatment. Drug identity (name, strength) is included in the label text; random code/disclosure envelopes or lists are not provided.

## **9.4 Storage and Handling Requirements**

Clinical supplies must be stored in a secure, limited-access location under the storage conditions specified on the label.

Receipt and dispensing of trial medication must be recorded by an authorized person at the trial site.

Clinical supplies may not be used for any purpose other than that stated in the protocol.

## **9.5 Discard/Destruction>Returns and Reconciliation**

The investigator is responsible for keeping accurate records of the clinical supplies received from the Sponsor or designee, the amount dispensed to and returned by the subjects and the amount remaining at the conclusion of the trial. For all trial sites, the local country Sponsor personnel or designee will provide appropriate documentation that must be completed for drug accountability and return or local discard and destruction if appropriate. Where local discard and destruction is appropriate, the investigator is responsible for ensuring that a local discard/destruction procedure is documented.

# **10.0 ADMINISTRATIVE AND REGULATORY DETAILS**

## **10.1 Confidentiality**

### **10.1.1 Confidentiality of Data**

By signing this protocol, the investigator affirms to the Sponsor that information furnished to the investigator by the Sponsor will be maintained in confidence, and such information will be divulged to the institutional review board, ethics review committee (IRB/ERC) or similar or expert committee; affiliated institution and employees, only under an appropriate understanding of confidentiality with such board or committee, affiliated institution and employees. Data generated by this trial will be considered confidential by the investigator, except to the extent that it is included in a publication as provided in the Publications section of this protocol.

### **10.1.2 Confidentiality of Subject Records**

By signing this protocol, the investigator agrees that the Sponsor (or Sponsor representative), IRB/ERC, or regulatory authority representatives may consult and/or copy trial documents in order to verify worksheet/case report form data. By signing the consent form, the subject agrees to this process. If trial documents will be photocopied during the process of verifying worksheet/case report form information, the subject will be identified by unique code only; full names/initials will be masked prior to transmission to the Sponsor.

By signing this protocol, the investigator agrees to treat all subject data used and disclosed in connection with this trial in accordance with all applicable privacy laws, rules and regulations.

### **10.1.3 Confidentiality of Investigator Information**

By signing this protocol, the investigator recognizes that certain personal identifying information with respect to the investigator, and all subinvestigators and trial site personnel, may be used and disclosed for trial management purposes, as part of a regulatory submissions, and as required by law. This information may include:

- name, address, telephone number and e-mail address;
- hospital or clinic address and telephone number;
- curriculum vitae or other summary of qualifications and credentials; and
- other professional documentation.

Consistent with the purposes described above, this information may be transmitted to the Sponsor, and subsidiaries, affiliates and agents of the Sponsor, in your country and other countries, including countries that do not have laws protecting such information. Additionally, the investigator's name and business contact information may be included when reporting certain serious adverse events to regulatory authorities or to other investigators. By signing this protocol, the investigator expressly consents to these uses and disclosures.

If this is a multicenter trial, in order to facilitate contact between investigators, the Sponsor may share an investigator's name and contact information with other participating investigators upon request.

### **10.1.4 Confidentiality of IRB/IEC Information**

The Sponsor is required to record the name and address of each IRB/IEC member that reviews and approves this trial. The Sponsor is also required to document that each IRB/IEC meets regulatory and ICH GCP requirements by requesting and maintaining records of the names and qualifications of the IRB/IEC members and to make these records available for regulatory agency review upon request by those agencies.

